Mean Arterial Pressure: It is an average pressure present in the arteries in one cardiac cycle calculated by addition of diastolic blood pressure with 1/3rd of the pulse pressure.

Boezaart Score: 5

Grades Assessment

- 0- No bleeding (cadaveric conditions)
- 1- Slight bleeding: no suctioning required.
- 2- Slight bleeding: occasional suctioning required.
- 3- Slight bleeding: frequent suctioning. Bleeding threatens surgical feld a few seconds after suction is removed.
- 4- Moderate bleeding: frequent suctioning required and bleeding threatens surgical field directly after suction is removed.
- 5- Severe bleeding: constant suctioning required; bleeding appears faster than can be removed by suction; surgical field severely threatened and surgery usually not possible.

Methods & Materials

Study Design: Randomized controlled trial

Study Setting: Department of ENT, Benazir Bhutto Hospital

Study Duration: After the approval of the topic till completion of sample size

Sample Size:

By using WHO sample size calculator

Sample size n = 60 (30 in each group)

Level of significance = 5%

Power of test = 90%

Test value population mean = 1.96⁵

Anticipated population mean = 2.64⁵

Population standard deviation = 0.685⁵

Sampling Technique: Simple random sampling

Sample Selection

Inclusion Criteria

Patients bilateral chronic rhinosinusitis refractory to medical treatment and requiring surgical intervention.

Exclusion Criteria

- 1. Patients with malignancies.
- 2. Patients with unilateral disease
- 3. Bleeding diathesis
- 4. Uncontrolled hypertension
- 5. Long term usage of NSAIDS and anti-coagulants.

Data Collection Procedure

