This research will be carried out after approval from the Ethical Review Board of Rawalpindi Medical University. Patients requiring surgical intervention for chronic rhinosinusitis will be selected via simple random sampling. They will be divided into 2 groups via randomization (30 patients in each group) and undergo endoscopic sinus surgery in the operation theatre of Benazir Bhutto Hospital. Double blinding will be done. Surgery will be performed by a consultant with an experience of more than 5 years. For the intervention, normal saline will be warmed in a boiler up to 50°C and temperature will be continuously checked with the help of a thermometer. Group A will have irrigation of nasal cavities with hot normal saline (of 50°C) during the operation. Group B will have irrigation with saline at room temperature. This is a double blinded RCT in which the patient and the operating surgeon will not know about the specific intervention. Bleeding score will be checked via Boezaart score. More over, duration of the procedure and mean arterial pressure of all patients will also be documented. The researcher will collect the data by herself to avoid bais.

Data Analysis

Data will be analysed with help of SPSS version 26. Qualitative variables will be represented as frequencies and percentages. Quantitative variables will be represented via mean and standard deviation. Chi square test will be applied. Furthermore, logistic regression will be done. Data will be documented in tabular form. A P-value of <0.05 will be considered significant.

References

- 3. Alkan A, Honca M, Alkan A, Güleç H, Horasanlı E. The efficacy of esmolol, remifentanil and nitroglycerin in controlled hypotension for functional endoscopic sinus surgery. Braz

- J Otorhinolaryngol. 2021 May-Jun;87(3):255-259. Doi: 10.1016/j.bjorl.2019.08.008. Epub 2019 Oct 3. PMID: 31668787; PMCID: PMC9422684.

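### The trial is sized on a difference in mean Boezaart score, but Data Analysis names only a chi-square test and an unspecified logistic regression, so no stated analysis tests that difference

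*Combined protocol and SAP*

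**What the plan says.** **Sample Size** (Methods & Materials) lists a test mean of 1.96, an "Anticipated population mean" of 2.64, an SD of 0.685, 5% significance and "Power of test = 90" per cent, giving 60 patients, 30 per group. The Introduction shows where these come from: a cited study's operative-field result, 1.96 (SD 0.67) with hot saline against 2.64 (SD 0.70) in controls. The block does not name the Boezaart score. However, its means carry the same citation number as the Boezaart scale, which is the only bleeding or operative-field score in the plan.

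**Data Collection Procedure** states "Bleeding score will be checked via Boezaart score". The scale has six ordered grades, 0 to 5. It continues: "More over, duration of the procedure and mean arterial pressure of all patients will also be documented".

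**Data Analysis** describes data by type; for measured variables, "Quantitative variables will be represented via mean and standard deviation". The inferential content is three sentences: "Chi square test will be applied"; "Furthermore, logistic regression will be done"; and "A P-value of <0.05 will be considered significant". None is tied to a variable. No t-test, rank test, trend test, effect estimate or confidence interval appears anywhere in the document.

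**The concern.** The quantity used to size the trial and the tests named to analyse it do not meet. If the score is treated as quantitative, the plan summarises it but names no test for it. If it is treated as qualitative, chi-square applies, but that test compares whole distributions of unordered categories. It does not test the mean difference of 0.68 that justified 30 per group.

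The table layout is also open. Six grades can be left as they are, collapsed, or split in two, and the plan fixes none of these. Two analysts following Data Analysis faithfully could run different primary tests and reach different conclusions, and the choice could be made after the scores are known. The single significance rule, attached to no outcome, does not prevent this.

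Duration and mean arterial pressure could enter a chi-square test only after arbitrary grouping.

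**Working it through.** **1. The plan's own figure.** Inputs from Sample Size: difference 2.64 − 1.96 = 0.68; SD 0.685 (the root mean square of 0.67 and 0.70); alpha 5%, taken as two-sided because the plan does not say; power 90%.

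n per group = 2 × (1.960 + 1.282)² × 0.685² / 0.68² = 21.3, so 22 per group and 44 in total. The stated 60 does not follow from the stated inputs. That is a separate matter, and it errs towards a larger trial.

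**2. Power for the quantity the trial was sized on, at 30 per group.** Standard error = 0.685 × √(2/30) = 0.177. Then 0.68/0.177 − 1.960 = 1.88, which gives 97.0% power (96.6% by the exact t calculation). A comparison of means is amply powered.

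**3. An assumed grade distribution.** The documents give means and SDs but no grade frequencies, so these must be assumed. Discretised normals on grades 0–5, solved to match 1.96 (SD 0.67) and 2.64 (SD 0.70), give:

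| Grade | 0 | 1 | 2 | 3 | 4 | 5 |
|---|---|---|---|---|---|---|
| Hot saline | 0.008 | 0.216 | 0.590 | 0.181 | 0.006 | 0.000 |
| Control | 0.000 | 0.037 | 0.376 | 0.498 | 0.087 | 0.002 |

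**4. Power of the possible analyses**, by simulation at 30 per group, two-sided 5%:

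| Analysis of the score | Power |
|---|---|
| t-test | 97% |
| Mann-Whitney | 96% |
| Proportional-odds model | 96% |
| Chi-square, full grade table | 86% |
| Chi-square, grades 0–1 / 2 / 3+ | 91% |
| Chi-square, split at ≥3 | 91% (86% continuity-corrected) |
| Chi-square, split at ≥2 | 64% (40% corrected) |
| Chi-square, split at ≥4 | about 23–24% (4% corrected) |
| Binary logistic, likelihood ratio, split at ≥3 | 92% |
| Binary logistic, likelihood ratio, split at ≥2 | 67% |

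Hand check of the ≥3 split: the proportions are 0.186 and 0.587, with average 0.387. (0.4006 × √30 − 1.960 × √(2 × 0.387 × 0.613)) / √(0.186 × 0.814 + 0.587 × 0.413) = (2.194 − 1.350)/0.628 = 1.345, which gives 91%.

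On this distribution the full-table chi-square is 4 points under the stated 90% and 11 points under the t-test.

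**5. Sensitivity.** Simply rounding the normals to whole grades gives 94% for the t-test and 77% for the full table. The SDs there are 0.73 and 0.76, larger than the plan's, so part of that drop is added variance and not a cost of chi-square.

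**6. Type I error.** With both groups given the same distribution (the control shape or the pooled shape), the full-table chi-square rejects in 3.4–3.7% of trials. It is valid and somewhat conservative. Taking the smallest p-value from the full table, 0–1/2/3+ and the ≥3 split gives 7.0–8.2% uncorrected, or 5.4–6.5% if the two-group split is continuity-corrected.

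**The case against.** Several points on the other side are sound.

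- **Chi-square is a legitimate test for a graded score.** It is, and its error rate holds if the table is fixed in advance. What it does not do is use grade order or test the mean.
- **Logistic regression might be ordinal.** A reader might infer that neither named method uses the order of the grades. The documents do not support that: they give no outcome and no form, so the use of order is undetermined. A proportional-odds model would use it, with about 96% power here.
- **The trial is larger than it needs to be.** A reader might infer that the trial is underpowered. For a comparison of means it is not: 30 per group exceeds the 22 required. On the assumed distribution, several of the open choices also reach 90%, among them the three-group table, the uncorrected ≥3 split and a logistic model at ≥3.
- **The worst figures rest on unlikely choices.** No section suggests the ≥4 split. A type I error of 12–14% can be obtained by selecting among five uncorrected groupings, but only if that split is one of them. The 7–8% above is itself a ceiling, because it assumes the smallest p-value is always chosen.
- **A t-test may have been intended.** Possibly, but the plan names its tests and this is not among them. Presenting means and SDs is description, and a mean difference that could be derived from them is not a pre-specified comparison.

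These points limit the size of the numerical loss. They do not supply the missing primary analysis.

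**Conclusion.** The point holds and needs correcting before analysis. The plan is sized on a mean difference, names no test of means or ranks, and leaves both of its named methods without an outcome or a layout. That rests on the text alone and needs no distributional assumption.

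The size of the consequence does need one. With grades distributed to match the stated means and SDs, and no dropout, the full-table chi-square has about 86% power against 97% for a t-test, and two-group splits run from about 23% to 91%. The loss of power alone would be a modest criticism. The seriousness comes from the unnamed primary analysis and from the freedom to choose a grouping after seeing the scores.

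**What to change.** Replace the chi-square and logistic sentences in Data Analysis with:

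> The primary analysis compares the Boezaart score between Groups A and B with a two-sided two-sample t-test at 5%, reported as mean difference with 95% CI; a Mann-Whitney test is supportive. Duration and mean arterial pressure, where compared, use the same method and are secondary. Chi-square (or Fisher's exact test if expected counts are below 5) is used only for categorical variables.

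Mann-Whitney, or a proportional-odds model named as such, is equally acceptable as the primary analysis. What matters is that exactly one is fixed before scores are seen. Drop the binary logistic regression, or label it exploratory with no confirmatory claim at P<0.05.

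The wording assumes one score per patient. The plan does not say when the score is taken, and that should be settled at the same time.

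At SD 0.685 the 95% CI would be about ±0.35 grade (2.002 × 0.685 × √(2/30) = 0.354) around an expected difference of 0.68.

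The cost is wording only: no extra patients or data. The document is dated 16 May 2023 and does not give trial status. If scores have already been seen by group, the change should be dated and reported as made after that point.
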